### 8.2.2. Exclusion Criteria

Patients meeting any of the following criteria will not be included in the study:

1. Patients with claims for other conditions for which biologics are used during the one-year pre-index period or on the index date: ankylosing spondylitis, Crohn's disease, psoriasis, psoriatic arthritis, or ulcerative colitis will be excluded from the study.

**Table 1. Exclusionary Diagnoses**

Disease	ICD-9 diagnosis code	ICD10 diagnosis code
Ankylosing Spondylitis	720.0x	M45.*
Crohn's Disease	555.xx	K50.*
Psoriasis	696.1x	L40.0*-L40.4*, L40.8*-L40.9*
Psoriatic Arthritis	696.0x	L40.5*
Ulcerative Colitis	556.xx	K51.*
Juvenile Rheumatoid Arthritis	714.3*	M08.*

2. Patients with evidence of the index medication during the one-year pre-index period will be removed from the analysis. Patients will be allowed to have been treated with other biologics approved for RA (Tumor-Necrosis Factor-alpha inhibitors (TNFi) [adalimumab (Humira), etanercept (Enbrel), certolizumab pegol (Cimzia), golimumab (Simponi), infliximab (Remicade)] and non-TNFi's with alternative mechanisms of action [abatacept (Orencia), and rituximab (Rituxan), anakinra (Kineret), tocilizumab (Actemra)]) during the one-year pre-index period.
3. Patients with 1 or more biologics on the index date will be removed from the study.
4. Patients with tofacitinib therapy prior to index.
5. Patients with 1 or more claims for injectable MTX (see Jcodes in [Annex 2.B.](#)) in combination with tofacitinib.

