### 8.2.1. Inclusion Criteria

This study will include individuals who are privately insured and with Medicare Supplemental insurance paid for by their employers and initiating tofacitinib in combination with MTX for RA between 01 January 2014 and 31 January 2017. To be included in the final study sample, patients must meet the following inclusion criteria:

1. At least one claim for tofacitinib between 01 January 2014 and 31 January 2017 (the identification period).

- a. **Medication index date.** The index date will be the date of the first claim for tofacitinib during the identification period.

*Note: Patients will have a variable length baseline of at least a year long. The baseline period will be censored at January 1, 2012 based on licensed data availability. The majority of baseline measures will use data from the 12 months immediately prior to the index date. Select measures will use data during the entire variable length baseline.*

- b. Tofacitinib initiation. Patients must have a 2nd claim for tofacitinib within 60 days of the end of the days supplied from their index claim (at least two claims with no 60 day gap).
- c. Oral MTX initiation. Patients must have an initial prescription for oral MTX in the period between 30 days prior to index date and 30 days following index date followed by a 2nd prescription for oral MTX within 60 days of the end of the days supplied from their initial MTX claim (at least two claims/administrations with no 60 day gap).

2. Presence of The International Classification of Diseases, 9th Revision, Clinical Modification (ICD-9 CM) code for RA (in any position) during the one-year pre-index period or on the index date. ICD-9 = 714.0x-714.4x & 714.81 or ICD10 = M05.\* & M06.0\*-M06.3\* or M06.8\*-M06.9\*.

3. At least 18 years old as of the index date.

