### 8.3. Cohort Assignment

Patients will be assigned to a study cohort based on MTX status following initiation of combination therapy with tofacitinib and MTX. The “MTX discontinued” cohort will contain patients who experience a gap in MTX therapy of >60 days within 12 months post-index. The “MTX interrupted” cohort will contain patients who experience a gap in MTX therapy of >60 days with 1 or more subsequent fills within 12 months post-index. The “MTX persistent” cohort will contain patients with no gap >60 days within 12 months post-index. If sample size is insufficient, the MTX “discontinued” and “MTX interrupted” cohorts may be combined.

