### 8.6.3. Treatment Patterns

- **Non-persistence.** A 0/1 flag will be created to identify if the patient is not persistent with tofacitinib before the end of the 12 month follow-up period.

Non-persistence will be identified based on a gap in treatment with the index medication or switching to another biologic.

Among patients with 1 year of follow-up, persistence through the end of the 1 year follow-up will be identified. Persistence will be identified based on the day supply (or presumed day supply) and fill dates of claims for the index medication (see [Table 2](#) for a listing of presumed day supplies). Persistence with the index medication will be defined as not having a gap in therapy of at least 60 days between fills/infusions. For retail pharmacy (RX) claims the day supply will be utilized. For Healthcare Common Procedure Coding System (HCPCS) claims a presumed day supply derived from the product label will be utilized. A gap of at least 60 days between the run-out date (service date + day supply-1) and the next service date will be considered non-persistence. Patients with early refills will be allowed to accumulate a stockpile of the index medication of up to 14 days for later use.

- **Post persistence treatment patterns.** Patients who are not persistent for the entire follow-up period will be classified into the following mutually exclusive categories based on the first occurrence of non-persistence: switch immediately, discontinue then restart, discontinue then switch, discontinue and never switch or restart.
  - **Switch immediately.** Patients will be classified as switching immediately if they initiate a non-index biologic before a 60-day gap in treatment is observed for the index medication.
  - **Discontinue then restart.** Patients will be classified as discontinuing and then restarting if there is a gap in the index therapy of at least 60 days and the first medication observed after the gap is the index medication.
  - **Discontinue then switch.** Patients will be classified as discontinuing and then switching if there is a gap in the index therapy of at least 60 days and the first medication observed after the gap is a biologic (including Tofacitinib) different from index medication.

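### Exclusion 5 (injectable MTX) has no time window and can be met only while on tofacitinib, so read literally it deletes patients on a follow-up event tied to persistence and cohort membership

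*Combined protocol and SAP*

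**What the plan says.** Exclusion 5 in section 8.2.2 (printed after Table 1) removes "Patients with 1 or more claims for injectable MTX" when used "in combination with tofacitinib". It gives no start or end date and does not define the combination.

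The other four exclusions close by the index date. Exclusion 1 applies "during the one-year pre-index period or on the index date", exclusion 2 to the pre-index year, exclusion 3 to the index date, and exclusion 4 to "Patients with tofacitinib therapy prior to index".

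Section 8.2.1 fixes index: "The index date will be the date of the first claim for tofacitinib during the identification period". Item 1c requires a first oral MTX fill within 30 days either side of index and a second fill within 60 days of that supply running out.

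Section 8.3 then says: "Patients will be assigned to a study cohort based on MTX status following initiation of combination therapy with tofacitinib and MTX". The discontinued and interrupted cohorts contain patients who "experience a gap in MTX therapy of >60 days within 12 months post-index"; the interrupted cohort also has a later fill. No route of MTX is named there.

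The non-persistence flag in section 8.6.3 is set to "identify if the patient is not persistent with tofacitinib before the end of the 12 month follow-up period". Persistence is part of the primary objective (section 7).

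**The concern.** Because index is the first tofacitinib claim and earlier tofacitinib is excluded, combined use of tofacitinib and injectable MTX cannot exist before index. Exclusion 5 is therefore a post-index criterion, and nothing in its text stops it short of month 12.

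Every eligible patient already has two oral MTX fills, so the rule mainly catches people who later add or move to injectable MTX. Take two patients who move on the same day. The one still on tofacitinib is deleted; the one who had already stopped is kept. Deletion thus depends on the persistence process itself, and also on the post-index MTX behaviour that defines the cohorts.

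The regression models and the decomposition in section 8.10 cannot correct this, because the deleted patients are not in the data. No sensitivity analysis addresses it and section 8.12 does not list it as a limitation. Perfect coding of injectable claims would not remove the selection.

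**Working it through.** The plan states no rate of injectable MTX use, no expected non-persistence and no sample size, so there is no figure to reproduce. All rates below are assumptions. Time is in years and tofacitinib stopping is exponential.

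**General relation.** Let p be 12-month non-persistence with everyone kept, f the share deleted, and q non-persistence among the deleted. The retained rate is R = (p − f·q)/(1 − f), which exceeds p only if q < p. With p = 50% and f = 10%, q = 30% gives (0.50 − 0.03)/0.90 = 52.2%; q = 50% gives 50.0%; q = 70% gives (0.50 − 0.07)/0.90 = 47.8%.

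**Model 1: a share s moves at a uniform time between days 60 and 335, with no effect on stopping.**
- λ = −ln(1 − p). The chance of still being on tofacitinib at the move is S = [exp(−60λ/365) − exp(−335λ/365)]/(275λ/365). Then f = s·S and q = 1 − (1 − p)/S.
- p = 40%: λ = 0.511, S = 0.763, q = 21.4%. With s = 10%, f = 0.0763 and R = (0.40 − 0.0763 × 0.214)/0.9237 = 41.5%. With s = 5% and 20%, R = 40.7% and 43.3%.
- p = 50%: S = 0.695, q = 28.1%. With s = 5% and 20%, R = 50.8% and 53.5%. Simulating the same model with 2,000,000 patients gave 53.6%, so the upper end of the bias is 3.5 to 3.6 points.

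**Model 2: injectable claims at a constant rate while on tofacitinib, with the stopping hazard multiplied by m afterwards.**
- μ = −ln(1 − s), f = μ/(λ + μ) × [1 − (1 − p)(1 − s)], and R = λ/(λ + μ) × [1 − (1 − p)(1 − s)]/(1 − f). R does not depend on m, because everything after an injectable claim belongs to deleted patients.
- Write d = λ + μ − mλ. Then q = 1 − μ·exp(−mλ)·[1 − exp(−d)]/(d·f). The rate with everyone kept is f·q + (1 − f)·R, and the bias is R minus that.
- Worked case, p = 50% and s = 10%: λ = 0.693, μ = 0.105, f = 0.132 × 0.55 = 0.0726, R = 0.868 × 0.55/0.9274 = 51.5%. For m = 1, 2 and 3, q = 31.1%, 50.6% and 63.2%; the full rate is 50.0%, 51.4% and 52.3%; the bias is +1.5, +0.1 and −0.9 points.

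Bias in percentage points, for s = 5% / 10% / 20%:

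| m | p = 30% | p = 50% |
|---|---|---|
| 0.5 | +0.9 / +1.9 / +4.0 | +1.2 / +2.5 / +5.2 |
| 1 | +0.6 / +1.2 / +2.6 | +0.7 / +1.5 / +3.2 |
| 2 | 0.0 / +0.1 / +0.3 | 0.0 / +0.1 / +0.3 |
| 3 | −0.4 / −0.8 / −1.5 | −0.4 / −0.9 / −1.6 |

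Here p is the rate at m = 1. With no link between the move and stopping (m = 1), the two models together give +0.6 to about +3.6 points.

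**Between cohorts.** Suppose there is no true difference, p = 40%, and 10% move under Model 1. If all movers are in the discontinued or interrupted cohorts, the contrast (those cohorts minus persistent) shifts by 41.5 − 40 = +1.5 points. If all are in the persistent cohort, it shifts by −1.5. If both cohorts lose equally, it shifts by 0. Section 8.3 does not settle which applies:
- If the gap means oral MTX, a mover who does not return to oral fills usually has a gap.
- If it means any MTX, a mover with no break over 60 days is MTX persistent.
- On either reading, a direct move after about day 305 (365 − 60) leaves no time for an oral gap of more than 60 days by day 365.

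**The case against.** The strongest defence is that the rule was meant more narrowly. The study title and sections 8.1 and 8.2.1 use the phrase about combination for the regimen being started, and item 1c gives that start a 30-day window on each side. Read in parallel, exclusion 5 only removes patients whose starting regimen included injectable MTX, and most of the problem goes away. That reading is reasonable, but exclusion 5 does not state it. A programmer following the text would search all of follow-up. If the narrow reading is intended, writing it down is the fix.

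A reader might also infer that the rule overstates non-persistence specifically in the cohorts that leave oral MTX, and so biases the comparison against MTX withdrawal. The documents do not support that. The upward direction needs deleted patients to stop tofacitinib less often than the rest, which fails if a move to injectable MTX precedes earlier stopping. The one-sided loss needs the gap to be in oral MTX, which section 8.3 does not say.

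The size may also be smaller than the illustration. Exclusion 5 points to the J-codes in Annex 2.B, so injectable MTX billed through pharmacy NDCs might not trigger it, and the deleted share could be below the range assumed here.

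**Conclusion.** The defect holds: as written, exclusion 5 is a whole-patient deletion on an undated post-index event that requires the patient to be on tofacitinib. It can bias retained persistence, and also PDC and effectiveness, since both depend on days covered by the index drug; those two were not quantified.

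If injectable use is unrelated to stopping, non-persistence within a cohort is overstated by about 0.6 to 3.6 points. This assumes 5% to 20% injectable use, 30% to 50% non-persistence and exponential stopping, none of which comes from the documents. The bias is near zero if the stopping hazard doubles after the move and is −0.4 to −1.6 points if it triples. The sign of the between-cohort bias is undetermined. This is a modest problem of unknown direction, worth correcting because the correction is cheap.

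**What to change.** 1. In 8.2.2, limit exclusion 5 to injectable MTX claims within the window already used in 8.2.1 item 1c (30 days before to 30 days after index). Using the whole pre-index year instead would make it a different criterion: it would newly exclude past injectable users who started tofacitinib on oral MTX, in a study that section 8.10.6 expects to be relatively small.
2. Keep patients whose first injectable claim comes after that window.
3. In 8.3, state that injectable MTX counts as MTX exposure when testing for the gap of more than 60 days, so that a change of route is not read as withdrawal.
4. Report the number of later injectable users by cohort, and repeat the primary comparison without them as a sensitivity analysis.

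The cost is a sentence in each of 8.2.2 and 8.3, one count and one extra run, with no new data. Item 3 also needs a short coding note: Annex 2.B does not separate its MTX J-codes by route, and Table 2 gives a presumed day supply for tofacitinib only, so the gap test needs a stated supply rule for injectable claims. The first 30 days after index remain a small post-index window. A few patients in an oral-MTX study will have injectable MTX during follow-up; the sensitivity analysis shows their influence.

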### 8.3. Cohort Assignment

Patients will be assigned to a study cohort based on MTX status following initiation of combination therapy with tofacitinib and MTX. The “MTX discontinued” cohort will contain patients who experience a gap in MTX therapy of >60 days within 12 months post-index. The “MTX interrupted” cohort will contain patients who experience a gap in MTX therapy of >60 days with 1 or more subsequent fills within 12 months post-index. The “MTX persistent” cohort will contain patients with no gap >60 days within 12 months post-index. If sample size is insufficient, the MTX “discontinued” and “MTX interrupted” cohorts may be combined.

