## 6. RATIONALE AND BACKGROUND

Tofacitinib was approved by the Food and Drug Administration (FDA) in November 2012 for the treatment of adult patients with moderately to severely active rheumatoid arthritis who have had an inadequate response or intolerance to methotrexate. It may be used as monotherapy or in combination with methotrexate (MTX) or other nonbiologic disease-modifying antirheumatic drugs (NB-DMARDs).

Pfizer is currently conducting a phase 3b/4 study (A3921192) which was designed to evaluate the sustained efficacy and safety of tofacitinib modified release formulation (11 mg QD) after withdrawal of MTX versus tofacitinib modified release formulation plus continued MTX treatment in subjects with moderate to severe rheumatoid arthritis who are insufficiently responding to their stable dose of methotrexate treatment. This retrospective claims analysis is designed to compare the effectiveness and treatment patterns among tofacitinib+MTX patients who withdraw MTX vs. continue MTX in a real world setting.

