### Primary Objective

- Compare treatment patterns including dosing, concomitant medication use, adherence, persistence, and switching among tofacitinib+MTX patients who withdraw MTX vs. persist with MTX or experience interrupted MTX.

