### 8.5. Period of Observation

All patients will be required to be continuously enrolled in the health plan for at least 24 months. Patients will have a variable length baseline period of at least 12 months. The 12 months prior to the index date will be used to assess the majority of pre-index characteristics. However, for select measures, eg, number of prior biologic therapies, and years since first RA diagnosis, the entire variable length baseline period will be utilized.

Measures utilizing the variable length baseline are noted. All baseline periods will be censored at January 1, 2012. The twelve months following the index date will be used to assess outcomes including treatment patterns, and health care costs, utilization and medication effectiveness.

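### MTX cohorts and outcomes are read from the same 12 months with no ordering rule, so the contrast describes the cohorts but cannot support an effect of MTX withdrawal

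*Combined protocol and SAP*

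**What the plan says.** - **Cohorts.** Section 8.3 classifies patients after index: "Patients will be assigned to a study cohort based on MTX status following initiation of combination therapy with tofacitinib and MTX". The discontinued cohort is "patients who experience a gap in MTX therapy of >60 days within 12 months post-index". The interrupted cohort has such a gap and a later fill, and the persistent cohort has no such gap.
- **Outcomes.** Section 8.5: "The twelve months following the index date will be used to assess outcomes including treatment patterns, and health care costs, utilization and medication effectiveness".
- **Tofacitinib non-persistence** (8.6.3) is a flag to "identify if the patient is not persistent with tofacitinib before the end of the 12 month follow-up period", and "Non-persistence will be identified based on a gap in treatment with the index medication or switching to another biologic". Switching, the glucocorticoid criteria (8.6.4) and costs (8.6.5) also run from the tofacitinib index date.
- **Entry.** Section 8.2.1 requires tofacitinib only through a second claim ("at least two claims with no 60 day gap").
- **Purpose.** The primary objective compares treatment patterns among "tofacitinib+MTX patients who withdraw MTX vs. persist with MTX or experience interrupted MTX". Section 6: "This retrospective claims analysis is designed to compare the effectiveness and treatment patterns among tofacitinib+MTX patients who withdraw MTX vs. continue MTX".
- **Analysis.** Section 8.10 summarizes treatment patterns by cohort and enters study cohort as a fixed covariate in the effectiveness model. Section 8.10.1 says multivariable techniques, decomposition included, will be used to compare outcomes. Section 8.10.6 offers decomposition as one possible solution and says it would separate the part of the effect caused by the drug from the part caused by patient differences.
- **Limitations.** Section 8.12 does not mention the shared window.

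**The concern.** Exposure and outcome are measured over the same months, and no rule says which must come first. Two patients show the consequence. One switches off tofacitinib in month 3 and lapses on MTX in month 7; the plan counts a withdrawal patient with tofacitinib failure, although the failure came first. Another stops tofacitinib early but keeps filling MTX; the plan counts an MTX-persistent patient with tofacitinib failure. In the same way, all costs before the MTX stop are charged to the withdrawal cohort.

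The only before/after split in the plan, for opioids and NSAIDs in 8.6.2, is by persistence, which 8.6.3 defines for tofacitinib and not for MTX. Covariates measured before index cannot restore an order of events that arises after index, so neither regression nor decomposition removes the problem. At stake is whether a reported difference may be read as something that follows MTX withdrawal.

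**Working it through.** The plan gives no sample size, rate or effect size, so there is no figure of its own to reproduce.

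**1. How much of the outcome window can precede withdrawal.** MTX may start at day -30 and needs two fills (8.2.1). With back-to-back fills, the earliest run-out is -30 + 2 × supply - 1: day 29 for 30-day fills and day 149 for 90-day fills. A gap above 60 days inside 365 days needs run-out by 365 - 61 = day 304. The share of the year before the MTX stop is therefore 29/365 = 8% (30-day fills) or 149/365 = 41% (90-day fills) at the least, and 304/365 = 83% at the most.

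**2. Non-persistence contrast when MTX withdrawal has no effect.** Assume constant hazards, 40% stopping each drug in the window if unlinked, no shared cause and no MTX resumption. The MTX-stop hazard is multiplied by k once tofacitinib has ended. Let A = B = -ln(0.6) = 0.511.

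- P(neither stops) = e^-(A+B) = 0.36.
- x = P(tofacitinib stops, MTX persistent) = A·e^(-kB)·[1 - e^-(A+B-kB)] / (A+B-kB). At k = 2 the limit is A·e^(-2B) = 0.511 × 0.36 = 0.184.
- Non-persistence among MTX persistent = x/(x + 0.36); among discontinued = (0.40 - x)/(0.64 - x).
- P(both stop, MTX first) = half of 0.40 × 0.40 = 0.08, whatever k is. The share of the discontinued cohort's failures that precede the MTX stop is 1 - 0.08/(0.40 - x).

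| k | x | Persistent | Discontinued | RR | Failures before MTX stop |
|---|---|---|---|---|---|
| 0.5 | 0.276 | 43.4% | 34.0% | 0.78 | 35% |
| 1 | 0.240 | 40.0% | 40.0% | 1.00 | 50% |
| 2 | 0.184 | 33.8% | 47.4% | 1.40 | 63% |
| 3 | 0.144 | 28.6% | 51.6% | 1.81 | 69% |

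**3. Wider assumptions.** A daily simulation with 30-50% stopping tofacitinib and 30-40% stopping MTX, with and without MTX resumption, gives null RRs of 0.72-0.83, 0.99-1.01, 1.27-1.46 and 1.50-1.86 at k = 0.5, 1, 2 and 3. Half of those runs allow stops from day 0, which the two-claim rule and the 30-day minimum supply in Table 2 exclude; later starts barely change the RRs. An unmeasured shared cause (log-normal, SD 0.8) gives 1.17-1.32 at k = 0.5 and 1.43-1.69 at k = 1.

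**4. Time-ordered alternatives (rate ratios).** Supply-state means that MTX status changes at run-out, with days 1-60 and later days off MTX as separate states. Confirmed-gap means that status changes only after 60 days off.

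| Truth | Supply-state | Confirmed-gap |
|---|---|---|
| No effect, no shared cause | 0.97-1.03 | 0.97-1.03 |
| HR 3 in first 60 days off MTX only | 2.95-3.05, then 0.96-1.04 | 0.75-0.84 |
| No effect, shared cause SD 0.8 | 1.24-1.41, then 1.64-1.87 | 1.60-1.78 |
| No effect, 5-10% stop both drugs together | 1.02-1.18 (days 1-60) | 0.75-0.95 |

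**5. Restricting gaps to those that begin on tofacitinib, same 12-month window.** At k = 1 in the example, the restricted cohort has probability 0.40 - 0.08 = 0.32 and non-persistence 0.08/0.32 = 25%. All others have 0.32/0.68 = 47%. The null RR is 0.53.

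**6. Day-180 landmark.** A completed gap needs MTX run-out by 180 - 61 = day 119. Two back-to-back 90-day fills run out at day 149 at the earliest, too late to qualify. For the rest, read the assumed rates as 365-day risks. The withdrawn share is P(MTX run-out by day 119) × P(on tofacitinib at day 180). Low end (tofacitinib 50%, MTX 30%, stops from day 60): 0.056 × 0.796 = 4.5%. High end (30%, 40%, from day 30): 0.117 × 0.864 = 10.1%. Removing patients who have resumed MTX brings this to roughly 5-8%.

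**The case against.** The strongest defence is that the plan states no sequential question. Sections 6 and 7 compare groups of patients who withdraw or continue MTX; the wording about efficacy after withdrawal in section 6 describes a separate phase 3b/4 study. Treatment patterns are only summarized, multivariable modelling of effectiveness is optional, modelled outcomes are to be chosen later, and decomposition is one possible solution. This stands in part. The cohort tables need no repair as description, and 8.10.6 cannot be treated as a settled analysis. It does not dispose of the point, because 8.10.1 says decomposition will be used when comparing outcomes, 8.10.6 would credit part of the difference to the drug, and 8.12 gives no warning.

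A second defence is that bias is not shown. That is correct for unlinked stopping, where the null RR is about 1. Every other value above rests on an assumed link or shared cause. Nor does counting costs before the MTX stop create a cost difference by itself; it dilutes a true one.

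A reader might infer that the plan makes withdrawal look worse. The documents do not support that: the RR falls below 1 when k is below 1 and there is no shared cause. Nor is this classic immortal time through death or censoring, since 8.5 requires continuous enrolment throughout.

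**Conclusion.** The point holds as a limit on interpretation. The whole-window contrast validly describes the three cohorts, but it mixes events before and after MTX withdrawal and cannot support an effect of withdrawal. With unlinked stopping and no true effect it is unbiased, although about half of the discontinued cohort's tofacitinib failures still precede the MTX stop. If tofacitinib stopping changes the chance of stopping MTX, or the two share a cause, it is biased. For assumed multipliers of 0.5 to 3 without a shared cause, the null non-persistence RR runs from about 0.8 to 1.8.

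Those figures are illustrative; the documents give no stopping rates and no link, so direction and size are unknown. They concern non-persistence. Effectiveness, utilization and costs share the overlap, but its size for dollar costs and utilization was not estimated. The change is worth making because it is cheap and settles what the study may conclude.

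**What to change.** 1. In 8.3, 8.10 and 8.10.6, label whole-window cohort comparisons as descriptive associations and remove the attribution to the drug for them. List the shared window in 8.12.
2. Base any statement about tofacitinib non-persistence or switching after MTX withdrawal on a time-to-event model with time-varying MTX status, ending at tofacitinib stop or switch and adjusted for baseline covariates. Use current MTX supply as the main definition: status changes at run-out, with days 1-60 and beyond 60 without supply as separate states. Keep the confirmed-gap version as a sensitivity analysis, because it counts the first 60 days off MTX as on MTX and can reverse an early effect.
3. For costs and utilization, a landmark among patients still on tofacitinib is optional and descriptive. If day 180 is used, state that two back-to-back 90-day MTX fills keep a patient out of the withdrawn group, and that this group would hold only about 5-8% of the starting sample under the assumed rates.
4. Do not restrict 8.3 to gaps that begin on tofacitinib while keeping the 12-month window. That adds immortal-time bias, which a shared cause may mask.

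The cost is extra programming on fill dates already held, and low precision in a sample that 8.10.6 expects to be relatively small. The time-ordered model gives no protection from unmeasured shared causes or from both drugs being stopped together; state this in 8.12. Its rate ratios should not be set directly against cumulative risk ratios from the whole-window tables.
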